  - q. This procedure is not required at the Early Termination visit in patients whose last dose of study drug was taken during Week 32 or earlier or within 4 weeks after completion of the Week 36 scan. However, the procedure may be done if it will aid in the evaluation of an ongoing adverse event.
  - r. Patients with a bone mineral density loss of > 3% at their Week 52/Early Termination visit (or most recent scan if the Week 52/Early Termination visit was not done) relative to parent study Baseline measurement will undergo a follow-up bone densitometry scan at 6 ( $\pm$ 1) months and will be contacted to question them about medications and conditions (eg, pregnancy) that might affect bone mineral density through the time of follow-up bone densitometry. The follow-up bone densitometry will be submitted for central reading.
  - s. Endometrial biopsies are to be done per instructions in the parent study. See the Laboratory Manual for guidance on handling and shipping the biopsy sample to the central laboratory for analysis. An endometrial biopsy will have been performed at the parent study Week 24 visit for all patients who participated in MVT-601-3101 only (see MVT-601-3101 protocol for details).
  - t. Please see [Appendix 1](#) for list of protocol-specified analgesics and see the Study Reference Manual for information on where and how to obtain protocol-specified analgesic medications by country. At the Week 52 visit, patients who will not be proceeding to another extension study will be re-dispensed or prescribed protocol-specified analgesic drugs, if needed, to ensure sufficient supply until the Follow-Up visit. For patients proceeding to another extension study, refer to the protocol for that next study.
  - u. Pregnancy test must be negative before the study drug dose is administered.
  - v. Patients will take the first dose of the study drug for this study once daily starting with the Week 24/Baseline visit (taken at the visit). The first dose of study drug for this extension study must not be taken until all parent study Week 24 procedures such as laboratory tests have been completed. Therefore, results of testing required for eligibility (eg, DXA) must be available on or prior to the Week 24/Baseline visit. The last dose of study drug will be taken in the clinic during the Week 52/Early Termination visit.

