#### 4.5. Removal of Patients from Therapy

Completion of the Week 52 visit defines completion of the study. Patients may withdraw consent to participate in the study and discontinue treatment at any time for any reason. Investigators or the medical monitor may remove patients from therapy under this protocol for reasons of safety and/or lack of compliance as discussed below. Patients removed from therapy for any reason will undergo the assessments for the Early Termination visit (see the Week 52 visit on the Schedule of Activities, [Section 1.1](#)) and will have a Follow-up visit to assess safety approximately 30 days after the end of study drug treatment (ie, after the patient's last dose of study medication). When patients complete the study or early terminate from the study, they must be deactivated from the study in the IVRS/IWRS, eDiary, and tablet device.

The following safety and/or compliance events will result in the removal of patients from therapy either permanently or until the etiology of the problem has been identified and resolved:

- Any adverse event that is intolerable to the patient and that cannot be ameliorated by the use of adequate medical intervention, or that in the opinion of the investigator or medical monitor would lead to undue risk to the patient if dosing continued;
- If it is discovered after enrollment that a patient failed to meet protocol entry criteria and continued participation poses an unacceptable risk to the patient's health;
- If the following liver test abnormalities develop, study drug should be discontinued immediately with appropriate clinical follow-up (including repeat laboratory tests, until a patient's laboratory profile has returned to normal/baseline status):
  - ALT or AST > 8 x ULN; or
  - ALT or AST > 5 x ULN and persists for more than 2 weeks; or
  - ALT or AST > 3 x ULN in conjunction with elevated total bilirubin > 2 x ULN or international normalized ratio (INR) > 1.5; or
  - ALT or AST > 3 x ULN with appearance of fatigue, nausea, vomiting, right upper quadrant pain or tenderness, fever, rash and/or eosinophilia (> 5%);
- QT interval by the Fridericia correction (QTcF) prolongation of more than 500 msec read by a cardiologist;
- Evidence of endometrial hyperplasia or endometrial carcinoma on endometrial biopsy;
- If the patient has a  $\geq 7\%$  loss of bone mineral density at lumbar spine, total hip, or femoral neck compared with the parent study Baseline;

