- If the patient, in the opinion of the investigator or the medical monitor, is grossly noncompliant with the protocol's requirements. Gross noncompliance includes < 75% compliance with the study drug over > 2 consecutive months; missing multiple study visits; and persistent (> 2 consecutive months) with < 50% of the required number of days of eDiary completion. Investigators will follow up with the patient and encourage compliance with study drug or eDiary prior to discontinuing her from the study;

- If the patient becomes pregnant at any time after providing a signed informed consent form, the patient must be withdrawn immediately (see [Section 7.8](#) for information on pregnancy reporting).

Should a patient fail to attend the clinic for a required study visit within the protocol-defined window, the site should attempt to contact the patient and reschedule the missed visit as soon as possible. The site should also counsel the patient on the importance of maintaining the assigned visit schedule and determine whether the patient can and/or should continue in the study based on previous noncompliance. In cases where the patient does not return for the rescheduled visit or cannot be reached to reschedule the missed visit, the site should make every effort to regain contact with the patient. The site should attempt at least three documented telephone calls and if necessary a certified letter to the patient's last known mailing address so that they can appropriately be withdrawn from the study with a primary reason of "Lost to Follow-up."

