### **6.3. Early Termination Visit and Follow-up Visit**

All patients withdrawing from the study prior to Week 52 will complete an Early Termination visit. The Early Termination visit procedures are identical to those of Week 52; however, for patients whose last dose of study drug is during Week 32 or earlier or within 4 weeks after completion of the Week 36 scan, the bone densitometry does not need to be performed. This procedure may be performed, however, at the investigator's discretion, if it aids in follow-up of an ongoing adverse event(s).

Patients (including those who complete the Week 52 visit and those who withdraw early from this study) will have a Follow-up visit approximately 30 days after the last dose of study drug, or prior to the date of initiation of another investigational agent or hormonal therapy affecting the hypothalamic-pituitary-gonadal axis or surgical intervention or other invasive procedure for endometriosis, whichever occurs first. However, for patients who enroll directly into another relugolix clinical study upon completion of the Week 52 visit, the Follow-up visit may be waived.

The Follow-up visit will be used to assess safety after discontinuation of study treatment including adverse events, clinical safety laboratories, and return of menstruation. Refer to the Schedule of Activities (see [Section 1.1](#)) for individual study visit procedures during the Follow-up visit.

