## **6.5. Study Procedures**

### **6.5.1. Efficacy-Related Procedures**

#### **6.5.1.1. Pharmacodynamics Sample Collection**

A blood sample for the pharmacodynamic analysis of serum estradiol will be collected pre-dose at the visits indicated in the study Schedule of Activities (see [Section 1.1](#)), other than at the Week 52 or the Early Termination visit, when no dose is administered. These pharmacodynamic samples will be analyzed at a central laboratory. These results will not be shared with the sites at any time.

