#### **6.5.2.6. Bone Mineral Density**

Bone mineral density is determined using DXA scanning and will be assessed at the lumbar spine (L1, L2, L3 and L4), total hip, and femoral neck (same leg within each patient) at the time points described in the Schedule of Activities (Section 1.1). The scans will be read by the central imaging laboratory in accordance with the imaging charter. Training, quality review, and readings will be done by a central radiology laboratory as described in the central radiology charter for bone mineral density.

Throughout the study, the same DXA apparatus will be used at each site and operated in the same scan mode for all scans for an individual patient and should be the same as used for the patient during the parent study (MVT-601-3101 and MVT-601-3102). The central core imaging laboratory will collect and evaluate all DXA scans for acceptability. Bone mineral density changes for individual patients will be monitored by the central imaging laboratory over the course of the study.

Patients with a bone mineral density loss of  $> 3\%$  at lumbar spine or total hip at their Week 52/Early Termination visit (or most recent scan if the Week 52/ET scan was not done) relative to parent study Baseline measurement will undergo another bone densitometry scan at  $6 (\pm 1)$  months and will be contacted to obtain information about medications and conditions (eg, pregnancy) that might affect bone mineral density through the time of the follow-up bone densitometry. The follow-up bone densitometry will be submitted for central reading.

Patients who experience a bone mineral density loss from the parent study Baseline of  $\geq 7\%$  at any of the anatomical sites assessed will be discontinued from the extension study and will undergo another bone densitometry scan as described above. Patients should be assessed for secondary causes of bone loss and followed up further if not improving on the 6-month follow-up scan, unless an alternative etiology has been identified.

If the patient enrolls directly into another relugolix clinical study upon completion of the Week 52 visit, then the follow-up bone densitometry scan at  $6 (\pm 1)$  months conducted under this protocol may be waived.

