## **7.8. Pregnancy Reporting**

If any patient becomes pregnant during the study, the site must discontinue the patient from the study treatment immediately and have her return for an Early Termination visit.

If the patient agrees, the investigator should notify the patient's primary care physician of the pregnancy and provide details of the patient's participation in the study and treatment.

A pregnancy is to be reported to the sponsor within 24 hours of awareness by the study site personnel, using the Pregnancy reporting forms and contact information in [Section 7.6](#). The expected date of delivery or expected date of the end of the pregnancy, last menstruation, estimated conception date, pregnancy result, and neonatal data, etc, should be included in this form, as available.

The investigator will follow the medical status of the mother, as well as the fetus, and will report the outcome to the sponsor.

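### Amendment 1 sends a woman withdrawn for pregnancy to an Early Termination visit that includes DXA, with waivers by date only and none for pregnancy; the follow-up scan has the same gap

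*Protocol*

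**What the plan says.** All references are to Amendment 1 unless stated.

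- **Section 4.5** sets the general rule: "Patients removed from therapy for any reason will undergo the assessments for the Early Termination visit". Pregnancy is one of its listed reasons: "If the patient becomes pregnant at any time after providing a signed informed consent form, the patient must be withdrawn immediately".
- **Section 7.8** repeats the instruction for pregnancy itself: "the site must discontinue the patient from the study treatment immediately and have her return for an Early Termination visit". It exempts no procedure.
- **Section 6.3** defines the content: "The Early Termination visit procedures are identical to those of Week 52". The Schedule of Activities and section 4.1 include bone densitometry by DXA at Week 52/Early Termination.
- **Section 6.3 and footnote q** waive the scan if the last dose was taken "during Week 32 or earlier or within 4 weeks after completion of the Week 36 scan". Even then the scan may be done to help evaluate an ongoing adverse event.
- **Section 6.5.2.6 and footnote r** require a further scan at 6 (±1) months when the loss exceeds 3%. Patients due for it are asked about "medications and conditions (eg, pregnancy) that might affect bone mineral density".
- **Dosing at the last visit.** Footnote v says: "The last dose of study drug will be taken in the clinic during the Week 52/Early Termination visit". Section 6.5.1.1, on the estradiol sample, says the pre-dose collection applies "other than at the Week 52 or the Early Termination visit, when no dose is administered". Section 5.4 has the Week 52 dose given in the clinic, and footnote n puts dosing after the pharmacodynamic sample.

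**The concern.** Read together, these sections order an x-ray scan of the spine and hip in a woman known to be pregnant, unless her last dose falls within a waiver. Pregnancy is foreseen: urine tests are monthly (4.6), contraception must be nonhormonal, and section 7.8 exists to manage the event. Yet the waivers are written only by date. Where DXA and pregnancy meet in the text, pregnancy is treated only as something that may affect the measurement.

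At stake is the safety of an individual patient and a clear instruction to sites. A site that sensibly omits the scan departs from the text, and section 10.2.2 does not allow deviation without sponsor approval (and ethics approval where required). No efficacy endpoint or bone-density conclusion is threatened.

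The dosing conflict is separate but arises at the same visit. One place puts a dose at Early Termination and another denies it, including for women whose drug was stopped at once.

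**Working it through.** **The chain of instructions**

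1. Pregnancy leads to immediate withdrawal (4.5).
2. Withdrawal for any reason, and pregnancy by name, leads to the Early Termination visit (4.5, 7.8).
3. That visit has the Week 52 procedures, including DXA (6.3, Schedule).
4. DXA is waived by date of last dose only (6.3, footnote q).
5. No sentence in the text shown removes DXA for pregnancy.

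The specific rule in 7.8 agrees with the general rule in 4.5, so neither overrides the other. Amendment 1 revised these waivers, adding the one tied to the Week 36 scan, and did not add pregnancy.

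**How much of the treatment period the waivers cover**

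Inputs: open-label treatment from Week 24 to Week 52 (section 6.2), and the two waivers in footnote q.

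- Treatment period: 52 − 24 = 28 weeks.
- First waiver: 32 − 24 = 8 weeks.
- Second waiver, with the Week 36 scan on schedule: 40 − 36 = 4 weeks.
- Waived: 8 + 4 = 12 weeks. Not waived: 28 − 12 = 16 weeks.

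Sensitivity:

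- Scan at Week 35 (window ±7 days): (35 − 32) + (52 − 39) = 3 + 13 = 16 weeks not waived.
- Scan at Week 37: (37 − 32) + (52 − 41) = 5 + 11 = 16 weeks not waived.
- If the Week 32 wording is read as covering one more week: 28 − 13 = 15 weeks not waived.
- Original protocol, which has only the first waiver: 28 − 8 = 20 weeks not waived.

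These are counts of calendar weeks by date of last dose. They show that the waivers do not remove the problem. They are not a probability that it occurs.

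**The follow-up scan**

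It falls 5 to 7 months after the last dose (6 ± 1), when a woman withdrawn for pregnancy may still be pregnant. Under Amendment 1 it can be triggered by the most recent scan if no Early Termination scan was done. A woman inside a date waiver can therefore still be sent for it.

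**The dose at the last visit**

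| Place | Week 52 | Early Termination |
|---|---|---|
| Section 5.4 | dose in clinic | not mentioned |
| Footnote v | dose in clinic | dose in clinic |
| Section 6.5.1.1 | no dose | no dose |

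Section 6.5.1.1 conflicts with 5.4 and footnote v at Week 52, and with footnote v at Early Termination. Footnote v also sits badly with the immediate stops in 4.5 (liver criteria) and 7.8 (pregnancy).

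**The case against.** **The text may be superseded.** The file lists Amendments 2, 3 and 3.1. The contents list and synopsis of Amendment 2 extend treatment to Week 104, so the Schedule and its footnotes were presumably reworked. This stands as a limit: the point is shown for the original protocol and Amendment 1 only. The week counts belong to the 28-week period.

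**The scan has a use.** A reader might infer that the scan serves no purpose in the woman's care. The documents do not support that: in 6.5.2.6 a loss above 3% triggers a follow-up scan, and a loss of 7% or more calls for a search for secondary causes. Hence the remedy is to defer any needed scan, not to drop bone follow-up.

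**The exposure cannot be sized.** A reader might turn the uncovered weeks, or a count of visits, into a risk. That is not supported. No number of pregnancies is given, visits move within their windows, and a scan at Week 52 belongs to study completion rather than early termination. No fetal dose or harm is estimated here.

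**Other safeguards.** The imaging charter or the Study Reference Manual may already bar the scan, and section 10.1.1 binds investigators to whichever standard protects the participant more. Many sites would probably omit the scan. This lowers the chance that it happens but leaves the protocol's instruction in place.

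**Dosing after an immediate stop.** One might infer that footnote v makes sites dose a pregnant woman or one stopped for liver tests. The specific stop instructions should prevail over a general footnote. What remains is a contradiction to tidy, not an order to dose.

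**Conclusion.** The point holds for the original protocol and Amendment 1. Outside the date waivers (about 12 of 28 weeks, so about 15 or 16 not covered under Amendment 1), the text requires DXA in a woman withdrawn for pregnancy. It makes no exception at the follow-up scan either. It should be corrected as a patient-safety matter; it changes no estimate or conclusion of the study.

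This rests on two assumptions that cannot be checked here: that the wording survives in Amendments 2 to 3.1, and that the imaging charter does not already exclude the scan. No size of risk is claimed. The contradiction over the last clinic dose is plain on the page but secondary.

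**What to change.** 1. In sections 6.3 and 6.5.2.6 and in footnotes q and r, add: *DXA is not performed in a patient with a positive pregnancy test or known pregnancy; any scan needed for bone-safety follow-up is deferred until after the pregnancy.* Refer to this from 4.5 and 7.8.
2. At the Week 36 and Week 52/Early Termination visits, do the scheduled urine pregnancy test before the DXA. Do not extend this order to Week 24/Baseline: DXA results must be available on or before that visit, so a scan done earlier would need an extra test.
3. Make footnote v, 5.4 and 6.5.1.1 agree: completers take the last clinic dose at Week 52 after the pharmacodynamic sample, and no study drug is given at an Early Termination visit. A statement about Early Termination alone would leave the Week 52 conflict in place.
4. Before drafting, confirm what Amendments 2 to 3.1 and the imaging charter say.

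The cost is a few sentences and cross-references. No procedure is added, because the urine test is already scheduled at these visits. The price is a missing or later bone-density value for the few women concerned.

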#### **4.6. Contraception/Pregnancy Avoidance**

In this study, medications and devices containing hormones for contraception are excluded, and patients must agree to use nonhormonal contraception throughout the study including through 30 days following the last dose of study drug, unless any of the following apply:

- Has a sexual partner(s) who was vasectomized at least 6 months prior to the Week 24/Baseline visit;
- Had a bilateral tubal occlusion (including ligation and blockage methods such as Essure™) at least 6 months prior to the Week 24/Baseline visit (patients with Essure must have prior confirmation of tubal occlusion by hysterosalpingogram) and there must be no evidence of post-Essure syndrome;
- Has a nonhormonal intrauterine device (eg, Paragard®) placed in the uterus;
- Is not sexually active with men; periodic sexual relationship(s) with men requires the use of nonhormonal contraception as described below;
- Practices total abstinence from sexual intercourse, as her preferred lifestyle; periodic abstinence is not acceptable.

The only acceptable methods of contraception for those for whom one of the above methods do not apply are:

- Condom (male or female condom) with or without spermicide (cream, spray, foam, gel, suppository, or polymer film);
- Diaphragm with spermicide (condom may or may not be used);
- Cervical cap with spermicide (condom may or may not be used); or
- Vaginal sponge impregnated with spermicide used with a condom.

Patients will be provided with information on acceptable methods of contraception as part of the informed consent process and will confirm with signing of the consent form that they understand the requirements for avoidance of pregnancy during the course of the study. Patients may not donate ova during the course of the study and for 2 months following the last dose of study drug.

A patient may start hormonal contraception 4 weeks after her last study dose of study drug provided her menstrual cycle has returned.

Urine pregnancy tests will be performed at monthly intervals during the study (including just prior to receiving the first dose of study drug), and patients will receive continued guidance with respect to the avoidance of pregnancy as part of the study procedures. Patients who become pregnant during the study will be withdrawn from the study and followed for pregnancy outcome (see [Section 7.8](#)).

## 5. TREATMENTS

### 5.1. Treatments Administered

In this extension study, all patients will receive the following open-label oral study treatment:

- 28 weeks of relugolix 40 mg tablet plus a capsule containing a tablet of 1.0 mg estradiol and 0.5 mg norethindrone acetate.

Each patient will be instructed to take one tablet and one capsule per day.

**Table 5-1 Description of MVT-601-3003 Study Drugs**

Name of Investigational Product	Relugolix	Estradiol / Norethindrone Acetate
Formulation Description	Round film-coated pink tablet	A Swedish orange, over-encapsulated round film-coated white tablet with back-fill material
Dosage Form	Tablet	Capsule
Unit Dose Strength	40 mg	Estradiol 1.0 mg / norethindrone acetate 0.5 mg
Route of Administration/ Duration	Oral once daily/ 28 weeks	Oral once daily/ 28 weeks

Two protocol-specified analgesics include a first-line non-steroidal anti-inflammatory drug (NSAID) and a second-line opioid or opioid/acetaminophen combination for endometriosis-related pain relief as required. The specific analgesic drugs offered may differ for different countries or regions. A list of study-specified analgesics is provided in [Appendix 1](#). For directions on prescribing rescue analgesic medications, see [Section 5.7](#).

### 5.2. Identity of Investigational Product

Relugolix has the chemical name 1-(4-{1-[(2,6-difluorophenyl)methyl]-5-[(dimethylamino)methyl]-3-(6-methoxypyridazin-3-yl)-2,4-dioxo-1,2,3,4-tetrahydrothieno[2,3-d]pyrimidin-6-yl}phenyl)-3-methoxyurea.

Estradiol (1.0 mg) and norethindrone acetate (0.5 mg) is a fixed-dose combination product.

